Families work with the therapist for a period typically lasting 4-6 months, following three stages. While the time in each stage and the time to completion varies significantly depending on the case and the family, we have outlined what the average case roughly looks like. It is important to note that MDFT is not rigid about the time spent in each stage, and transitioning between them can be porous. As such, these timelines are just guidelines based on previous cases and are not a measure of fidelity. This fluid approach ensures that therapists are responsive to the needs of each unique youth and family in traversing treatment stages, ensuring the programme is sensitive and appropriate for all participants, regardless of their demographic background.

Stage 1 (month 1): Therapists create an environment where the young person and their parents feel respected and understood. Therapists meet alone with each to begin the change process, establishing a strong therapeutic relationship which enhance motivation, reflection, and self-examination. Family sessions and community work also begin immediately upon starting MDFT to create systemic/relational change. Because these sessions are fundamentally directed at creating an environment of respect, it is here that any factors that

[figure not shown]
may play an important role within the therapeutic relationship and environment (such as considerations of ethnicity, sex, cultural or religious norms and practices and/or the intersectionality of such) will be addressed. Any such conversations will be led by young people/families, ensuring that individual agency is promoted and respected.

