Business as usual

Business as usual will be explored as part of the internal pilot study. There is a paucity of good quality intensive interventions for young people who use drugs. An initial scoping review of services, both statutory and non-statutory, has identified several organisations who provide services for young people who use drugs. Avon and Wiltshire Mental Health Partnership Trust has a specialist young person's substance use service that offers brief interventions such as motivational interviewing and motivational enhancement therapy for those at a high level of severity. Sessions, lasting approximately 45-minutes are offered weekly over a period of 2-4 weeks. Bristol Drugs Project offers 1:1 and group support over a 12-week period. In Newport, Barod offer 1:1 support and peer group sessions over 6-week period addressing alcohol and

drug use, harm reduction and psychoeducation. Gwent Drug and Alcohol Service also offer some support to YP although most of their support is targeted at adults.

Young people who are referred to the Front Door of both Newport and Bristol for reasons that fit with the eligibility criteria of this bid and who are placed in the control group, will not be offered any therapeutic intervention akin to MDFT, BAU is provided by other services rather than Barnardo's so MDFT therapists will not be involved in delivering BAU. They and their family may receive Family Support help which focusses on basic parenting skills and confidence and a "light tough" intervention directly with the young person. This might involve them being referred to a youth work provision which is most likely to be activity based with the aim of diverting them into more positive, pro-social use of their time. For some young people, there may be access to mentoring support, though this is dependent on geography and capacity, not all areas of Newport or Bristol have mentoring support, and it is in demand. It is usually delivered by a youth worker or volunteer and aims to involve young people in more positive activities and, at times, supports them to access education or training opportunities. MDFT differs significantly from BAU.

Impact evaluation

Research questions or study objectives

Primary research question

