- **PRQ6** To explore data redundancy at the 6-month end point to provide information on outcome assessments.
- PRQ7 To explore what constitutes business as usual across the two sites, Bristol and Newport.
- **PRQ8** To qualitatively explore the feasibility, acceptability and barriers associated with referral pathways with a particular focus on equity, diversity and inclusion.
- **PRQ9** To qualitatively explore intervention delivery and outcome assessments from the perspectives of participants, their family, intervention providers and key stakeholders.
- **PRQ10** To explore the cultural sensitivity of the intervention and trial methods and explore whether further adaption to the intervention is necessary.
- **PRQ11** To explore whether MDFT has any iatrogenic or unintended consequences.

Design

The study protocol has undergone an independent equality impact assessment (EIA) (appendix III). The EIA explores equity, diversity, and inclusion from a variety of perspectives. The EIA was coproduced with a Young Persons Advisory Group (YPAG). The MDFT intervention will undergo an initial adaption stage, coproduced with an advisory group who are representative of the population where the intervention will be delivered.

Information sheets, privacy notices and consent forms are designed to be understood and completed by young people. All outcome measures are validated for the age of the target population. Experts in the design of research for young people with intellectual disabilities, SEND and neurodiversity will be consulted to ensure the materials align with best practice. Where necessary translated materials will be prepared to meet the needs of a diverse ethnic population and where translated versions are not available, translators, including British Sign Language will be made available. Initial assessment will be conducted in a variety of Barnardo's and community locations that are accessible irrespective of disability status and young people will be encouraged to choose a location they find most comfortable. Follow-up assessments will be conducted using a video link and conducted by a researcher with experience of working with marginalised young people.

The recruitment of MDFT therapists will be conducted through local organisations and aim to reflect the diversity of the population where it will be delivered. Young people will be able to choose a therapist who their own cultural or ethnic background or protected characteristics.

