Wellbeing will be assessed using the Short Warwick-Edinburgh Mental Well-being scale (SWEMWBS; (Clarke et al., 2011)). SWEMWBS is a 7-item, self-completed scale addressing different aspects of eudemonic and hedonic mental health wellbeing. The scale is validated for adolescents and demonstrates good internal consistency (Ng Fat et al., 2017), and discriminant, construct and convergent validity (McKay and Andretta, 2017, Ng Fat et al., 2017).

We will use questions derived from a Client Service Receipt Inventory (CSRI; (Coulton S et al., 2023) to assess school, work and criminal justice involvement over the previous 6-months. All these outcomes will be assessed at baseline and again at month 6.

To explore the mechanism of change we aim to assess changes in domains that are key targets of MDFT. The Brief Family relationship Scale (BFRS; (Fok et al., 2014)) will be used to assess family conflict and cohesion. Motivation to change will be assessed using the readiness to change ruler (RR; (Maisto et al., 2011)). Self-efficacy will be assessed using the short Situational Confidence Questionnaire (SCQ-8;(Breslin et al., 1998)). Positive and negative Expectancy will be assessed using a four-item expectancy measure (SUE; (Montes et al., 2019)).

Secondary outcomes will be assessed at baseline and at the 6-and 12-month follow-up points and have established psychometric properties in adolescent population. Therapeutic alliance will be assessed using the revised Therapeutic Alliance Scale for Children (TASC-r; (Shirk and Saiz, 1992)) at the 6-month follow-up only.

All outcome measures have been used previously in adolescent populations, and we estimate the outcome data set takes on between 10 and 20 minutes to complete.

Table 4: Core outcomes and the time of data collection.

Outcome	No of items	Baseline	Six months
Stratification			
Global Assessment of Individual Need – short screen (GAIN-SS)	5	✓	
Covariate			
Single Substance Use Question – 28 day (SUSQ28)	1	✓	
Primary			
Time Line Follow-Back – 28 (interview)			✓
Secondary			
Self-reported delinquency (SRDS) ¹	36	✓	✓
Strength and Difficulties (SDQ) ¹	25	✓	✓
Wellbeing (SWEBWMS)	7	✓	✓
Family cohesion and conflict (BFRS)	15	✓	✓
Alcohol and substance use problems (ESPAD)	8	✓	✓
Client Service Utilisation (CSRI)	8	✓	✓
Exploratory			
Motivation to change (RR)	1	✓	✓
Substance use expectancy (SUE)	4	✓	✓
Substance use efficacy (SCQ8)	8	✓	✓
Therapeutic Alliance (TASC-r)	12		✓

¹SRDS and SDQ are YEF core outcomes.

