We will ensure participants do not feel coerced to consent. Once a participant is referred to the service any consent to participate in the trial is theirs solely to make. Not consenting to the research will not impact on the BAU they receive, and this will be explained verbally and in writing. If a participant does consent it will be made clear that they can withdraw consent at any time.

We will minimise the potential for participants and staff to experience any adverse or iatrogenic events. In our experience of conducting similar studies in similar populations the risk of adverse events is low, as is the risk of iatrogenic events. We will implement a standard operating procedure for the reporting of adverse events that involves an independent

experienced third-party making recommendations on the severity of any event and whether they are associated with the trial. All staff involved in the study will have enhanced DBS accreditation and will be familiarised with safeguarding practice and procedures.

University of Kent Social Research Ethics Identifier: SRE 1200

Barnardo's Research Ethics Committee Identifier: BREC (23)

Trial Registration: ISRCTN10024151

Data protection

All systems and personnel are approved for the management of clinical and sensitive data and are ISO certified to ISO27001 standard. This includes all physical systems, systems to detect intrusion, encryption of data from point of collection to storage, quality assurance and audit trails associated with any data collected. All identifiable data collected will be done with explicit consent and limited to data to allow participants to be contacted for follow-up. Data linkage will employ a unique identifier where the link to identifiable information will be stored on an encrypted secure database. Researchers will be trained to GCP standard and will comply with all relevant data protection legislation. Once final follow-up is completed, personally identifiable information will be deleted from the dataset held by the university and where consent to the trial has been granted encrypted data will be transferred to the Youth Endowment Fund data archive. Consent for transfer of data will be taken from those resident in England, and data used by DfE, name, DoB and postcode will be transferred. Data collection and management will be governed by a trial specific Standard Operating Procedure agreed and approved by ethics.

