Young people may not want to consent to being part of study resulting in lack of numbers for the evaluation	Young people will have access to a clear information sheet highlighting the need to evaluate a new service. Information will be reviewed by a young person's advisory group who will provide input on how best to engage young people in the research. Our experience of other studies with similar populations is that many young people are motivated by altruism, the opportunity to contribute to services that will help others in a similar position in the future.

The potential that young people, therapists and researchers experience negative impacts of participating in the study.	All staff and researchers have access to supervision to raise issues relating to the trial. We will implement a reporting system to allow all staff, young people and their carers and researchers to highlight any potential adverse events and, if needed, seek support. We will implement an independent DMEC to review adverse and iatrogenic effects as they arise and if they believe these are directly attributable to the trial and severe in nature, they will raise the potential of stopping the trial with the research team and funder.
Families may be resistant to participating in the trial.	We have extensive experience of including marginalised populations in evaluations. The pilot study will explore qualitatively barriers to participation. All information about the trial will be available in advance of consent and potential participants provided an opportunity to discuss participation. Consent will be based on the consent of the young person rather than the family and early work in delivering MDFT identifies the most appropriate family members to be involved in the delivery of MDFT.
Young people may exhibit demoralisation if randomised to BAU rather than the MDFT intervention.	Clear information to participants that the study involves a state of equipoise, that at this stage we have no evidence that MDFT is better than BAU and this is what is being tested. Disengagement and 'faking bad' are key signs of resentful demoralisation and both concepts will be explored qualitatively with young people.

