Therapists need access to safe, supportive and therapeutic spaces within the community in which they can build relationships with children and families. Barnardo's has access to community buildings through partnerships with the Local Authorities, VCSE networks and youth work providers across Newport and Bristol. Local management are embedded within both Newport and Bristol, and are fully cognisant of local factors including geography, demography, need and support services, allowing us to target and understand the background and support needs of children and families, and access resources as required.

In Bristol, Barnardo's own a building at Old Market (Bristol Centre), which is located for ease of access to children and families. It has been decorated in co-production with young people who use it to be welcoming, therapeutic and trauma-informed throughout, and contains dedicated safe spaces for therapeutic delivery.

The MDFT team in each site usually consists of 6-8 therapists, one who is trained to act in a supervisory role. Training in MDFT is provided by MDFT international who provide an intensive training package and full certification. Training includes the assessment of the needs of children and families and case formulation to meet those needs. All therapists have access to supervisory support from the site based MDFT supervisor and the wider MDFT international team. MDFT therapists have access to the MDFT portal to record planned and delivered sessions.

Activities

The specification with respect to number of adolescent alone session, parent sessions without their adolescent, family sessions are guidelines are not dictates or requirements. The exact configuration is very individualised to the need of the young person and family. MDFT is not a curriculum-based intervention but instead is a psychotherapy where the exact interventions applied, types of sessions, weekly dose, length of treatment episode is determined by the needs of the young person and family. A minimum dosage is considered 12 sessions over a 4-month period.

MDFT typically consists of 2 sessions per week lasting anywhere from 45 to 90 minutes. 90 minutes may be necessary for multipart family sessions. Individual sessions alone with the young person typically range from 45 – 60 minutes, sessions alone with the parents are usually 60 minutes.

Mechanisms

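### Adverse events are collected by passive report only, with far more trial-linked contact in the MDFT arm, so between-arm harm comparisons are likely to be biased by unequal capture

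*Protocol*

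**What the plan says.** Capture of adverse events is described in two places. The Risks table (row on negative impacts of participating) says: "We will implement a reporting system to allow all staff, young people and their carers and researchers to highlight any potential adverse events". The ethics section adds: "We will implement a standard operating procedure for the reporting of adverse events", with an independent third party judging severity and relation to the trial. The same Risks row gives oversight to a committee: "We will implement an independent DMEC to review adverse and iatrogenic effects as they arise". Among the pilot objectives, PRQ11 is: "To explore whether MDFT has any iatrogenic or unintended consequences".

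On contact, the Intervention section states: "Families work with the therapist for a period typically lasting 4-6 months". Appendix I (Activities) adds: "MDFT typically consists of 2 sessions per week lasting anywhere from 45 to 90 minutes". For the control arm, the Business as usual section says: "BAU is provided by other services rather than Barnardo's so MDFT therapists will not be involved in delivering BAU". Research data collection is set for baseline, month 6 and month 12 (Longitudinal follow-ups), and the recruitment flow chart gives the two follow-ups to research staff blind to allocation. The scheduled instruments are in "Table 4: Core outcomes and the time of data collection", which lists no adverse-event form or question.

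**The concern.** A channel that waits for someone to report depends on how often someone is in a position to notice and report. In MDFT, therapists employed by the delivery partner see the young person and carers repeatedly for months. In BAU, the staff who see the young person work for other services, and nobody from the trial is scheduled to see them until the month 6 interview. At equal true risk, MDFT would then be expected to show more reported events, and discrete events in BAU would more often go unreported.

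At stake is any comparison of harms between arms, in the final report or under PRQ11. Unequal capture could make MDFT look harmful when it is not, or hide a real excess of events in BAU. A later analysis plan cannot repair this, because it cannot recover events that nobody asked about.

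**Working it through.** The protocol states no adverse-event rate, capture rate or harm comparison, so there is no figure of its own to reproduce. The check has three parts.

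**1. Contact by arm, randomisation to month 6**

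- MDFT, from the typical session counts in the Intervention section: individual 8–20, parent 4–10, family 4–10, community 4–10. Sum: 8 + 4 + 4 + 4 = 20 to 20 + 10 + 10 + 10 = 50.
- MDFT, from frequency: 2 per week over 4–6 months (17.3 to 26 weeks) gives 2 × 17.3 ≈ 35 to 2 × 26 = 52.
- Individual and family sessions alone: 8 + 4 = 12 to 20 + 10 = 30. Parent sessions still matter, since carers may report.
- BAU: no scheduled trial contact before the month 6 interview. Outside services do see these participants (one offers weekly sessions for 2–4 weeks), but they are not the delivery partner.
- Both arms then have the same interviews at months 6 and 12.

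**2. Whether the scheduled instruments fill the gap**

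- The ESPAD items in Appendix IV include accident or injury and hospital or emergency admission, but only as consequences of the respondent's own alcohol use, over 12 months. Drug-related and unrelated events fall outside, and at month 6 the window reaches back about 6 months before randomisation.
- The CSRI covers school, work and criminal justice; the SRDS covers offending.
- The SDQ and SWEMWBS are symptom and wellbeing scales, not event records.
- None of these asks about self-harm, emergency attendance unrelated to alcohol, or family or placement breakdown.

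**3. What unequal capture would do (illustration)**

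Reported events = n × true risk × capture probability. The arm size of 200 is from the protocol. The true risk of 20% in both arms and the capture probabilities are assumptions.

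| Capture, MDFT / BAU | Reported, MDFT | Reported, BAU | Apparent ratio |
|---|---|---|---|
| 60% / 40% | 200 × 0.20 × 0.60 = 24 | 200 × 0.20 × 0.40 = 16 | 1.5 |
| 80% / 30% | 200 × 0.20 × 0.80 = 32 | 200 × 0.20 × 0.30 = 12 | 2.7 |

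With equal true risk, the apparent ratio is simply the ratio of capture probabilities and does not depend on the risk: 0.60/0.40 = 1.5 and 0.80/0.30 = 2.7. Equal capture gives 1.0.

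In the second row, z = (0.16 − 0.06) / √(0.16 × 0.84/200 + 0.06 × 0.94/200) = 3.24, although there is no true difference. At the pilot's 30 per arm, the same assumptions give 30 × 0.16 = 4.8 against 30 × 0.06 = 1.8 events and z ≈ 1.25.

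**The case against.** The strongest reply is that the plan is only partly visible. The content of the operating procedure is not shown, and it might contain scheduled questions. Table 4 is headed as core outcomes, so a separate adverse-event form is not ruled out. That stands as a limit on certainty. Still, what the protocol says about the procedure concerns reporting and judging events, not asking about them, and no scheduled question appears anywhere.

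A reader might also infer several stronger things that the document does not support:

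- *BAU harms will go unseen.* The channel is open to young people and carers in both arms, and blinded researchers, who may use it, interview both arms at months 6 and 12. Escalating substance use is the primary outcome, measured alike in both arms, as are the SDQ, SWEMWBS, SRDS, CSRI and ESPAD. The Risks table also plans qualitative work on demoralisation. What remains is under-capture of discrete events.
- *Skewed counts would lead the DMEC towards stopping.* The stated rule turns on whether events are attributable to the trial and severe. No comparison of counts by arm is described.
- *PRQ11 cannot be answered.* It is an exploratory objective in a pilot of 60, and interviews will also explore unintended consequences. Those interviews, as described in the section on adapting MDFT, are with MDFT recipients and therapists, so they inform PRQ11 without supplying a comparison between arms.
- *The event counts will differ by a known amount.* Every risk and capture rate in the illustration is assumed.

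**Conclusion.** The concern holds as one of likely bias. The protocol describes passive reporting only, fixes no identical adverse-event questions in the two arms, and has about 20–50 delivery-partner sessions in MDFT against no scheduled trial contact in BAU before month 6. Reported events are likely to be more complete in MDFT, and discrete BAU events are likely to be under-captured. This affects the reading of harms between arms. It does not affect the primary outcome or the review of individual events.

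The direction rests on the contact schedule and on the operating procedure not already requiring the same questions of both arms. The size cannot be derived from the document. Apparent ratios of 1.5 to 2.7 illustrate what moderate and large differences in capture would do at equal true risk.

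**What to change.** Add a short adverse-event checklist covering the previous 6 months, worded identically for both arms, to the blinded month 6 and month 12 interviews. Ask it after the timeline follow-back. Suitable items would be emergency attendance or admission from any cause, self-harm, serious injury or assault, and family or placement breakdown. State in the protocol and the operating procedure that the checklist is the main source for between-arm comparisons of harm in the report.

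Keep spontaneous reports for safeguarding and for the DMEC's continuing review of individual events. Tabulate them separately by arm and by source, with a caution about unequal contact. The DMEC should not be confined to the checklist, because that would leave it without comparative information before month 6.

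The cost is about 2 minutes per interview at contacts already planned. There is some risk that answers disclose allocation, which asking after the primary outcome limits for that outcome at that interview. The checklist also gives nothing on those lost to follow-up: by the flow chart, 200 − 182 = 18 per arm at month 6 and 200 − 160 = 40 per arm at month 12. If the operating procedure already contains such questions, a sentence in the protocol saying so would suffice.
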